Pregnant Couple Members attending LFLS. All S&S+LFLS study participants will be followed from enrollment to six months post-partum (maximum ~ time of participation based on enrollment at ~3-4 months pregnant = 12 months). Participants will complete baseline, pre-and post-partum and 6-months post-partum assessments and attend the Spear & Shield and 2 LFLS intervention sessions (see below).

Enrollment will be conducted from month 7 – 24, a total of 18 months.

11) **Study Endpoints***

Primary and secondary study endpoints.

Primary endpoints.

- EIMC uptake (infant)
- VMMC uptake (father and other sons)

Secondary endpoints.

- Father's and mother's circumcision attitudes

Primary or secondary safety endpoints.

This is a behavioral feasibility study, not requiring safety endpoints.

12) **Procedures Involved***

Design.

Like Father Like Son(s) proposes to develop intervention materials and test the effectiveness of the intervention to enhance the uptake of early infant male circumcision (EIMC) and voluntary medical male circumcision (VMMC) in the community health center (CHC) setting.

The study utilizes a longitudinal repeated measures design [2 (condition) x 4 (time points)]. The pilot study intervention will expand the Spear & Shield (S&S) intervention to include the “Like Father Like Son” component (S&S + LFLS).

IRB Study Number:

Version #, Date:

The pilot study will randomize 8 clinics to Experimental and Observation conditions; clinics will be matched on catchment area size and current EIMC and VMMC rates.

Experimental clinics (n = 4) will be trained to offer “S&S+LFLS”; Observation clinics (n = 4) will be “Observation Only” sites. Observation only sites will not recruit participants and will only be “observed” regarding the total number of VMMCs and EIMCs conducted at each individual clinic - Observation Only clinics will only provide clinic level aggregate data.

The study will train both Experimental and Observation Only clinic staff to conduct VMMC and EIMC procedures in order to provide equivalent services at all clinics, controlling for the availability of circumcision at all sites. Participants will only be recruited from experimental sites. The study will also assess the feasibility and acceptability of offering S&S+LFLS at the CHC level, and if successful, plan for a clinical trial of the S&S+LFLS intervention.

CAB Meetings & Focus Groups.

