CAB Members associated with each CHC will thereby facilitate the adaptation of the intervention strategies to the local culture and clinic culture, enabling LFLS to work with the community rather than imposing the program on the community.

No personal, individually identifying information will be collected and no individual interviews or assessments will be conducted with CAB Members.

Focus Group Discussion (FGD) Members. FGD members will meet in gender concordant groups in a private room within their experimental clinic site; members will provide input on cultural factors that influence attitudes, perceptions, and beliefs about EIMC among pregnant couples.

They will provide guidance on cultural attitudes, ethnic preferences, beliefs and perceptions surrounding EIMC among pregnant couples in Lusaka. FGD members will inform the study on local issues or community concerns that could influence program uptake. No personal, individually identifying information will be collected and no individual interviews or assessments will be conducted with FGD members.

Couples Assessments.

Assessments at baseline will be completed using audio computer-assisted self-interview (ACASI) software, with support from study staff as needed. Participants will be assessed individually in a private office in the CHC; ACASI headphones and touchscreen computers will provide confidentiality and privacy. LFLS session 2 will be scheduled to coincide with the post-partum neonatal clinic visit in the first week following birth.

Each assessment measure (see attachment) is related to the study theoretical model, outcomes (feasibility, acceptability, uptake) and associated factors (e.g., plans, knowledge, norms, attitudes/beliefs and cultural or religious values associated with EIMC/VMMC, family decision making, stage of readiness).

After each LFLS session, a brief paper-based questionnaire will be individually administered to assess Stage of Change. VMMC/EIMC uptake and the role of parents, family members, peers and HIV serostatus in decision-making will be assessed by telephone or office visit at 6 months post-partum.

Couples intervention.

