influential other, if desired. EIMC brochures will be distributed and Stages of Change questionnaires will be administered prior to the session

Topics: Why undergo EIMC? What are the benefits? Why now? When is the best time for EIMC? Information: What happens? How long does it take? Is it painful, how is pain controlled? What happens next? How long is healing, cleaning during healing? What happens to the foreskin? What are the risks? Is it safe? Who should be involved in the decision? Any additional questions or concerns about EIMC?

Session 2 will include the opportunity for couples to bring a person culturally connected to making the EIMC decision to the session (e.g., paternal mother) (Mavhu et al., 2017). To enhance acceptability, LFLS sessions will be developed from CHC CAB members, focus group discussions, and health care staff. Content will be pertinent to the critical cultural, social and religious issues and beliefs affecting EIMC decision making, and will consider research in Zambia on this topic (e.g., Waters et al., 2012; 2013). The two LFLS sessions will be manualized, based upon the community input, and “fine-tuned” using feasibility pilot data. The preliminary outline, from focus discussions in Zambia, is proposed below.

Topics: Any new questions or concerns about EIMC? How does EIMC differ from VMMC? What is the religious view on EIMC? What does my culture say about MC? What was the purpose of the foreskin? (How long is it needed?) Will EIMC affect future sexual performance, functioning & potency? Final questions? Stages of Change questionnaires are administered prior to the session.

Location. All research procedures will be performed at the clinic sites, in private offices and meeting rooms.

Risks.

There are no drugs or devices used in this study; all procedures discussed (EIMC, VMMC) are available for uptake at the clinics and are evidence based practices.

Procedures to lessen the probability or magnitude of risks.

Source records used to collect data. All surveys, scripts, and data collection forms are being developed during the formative period of this study.

Proposed Assessments at baseline (see attachment for initially selected assessments):

Instruments will be adapted from S&S1 and previous VMMC/EIMC studies (~45 minutes).

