H2. Assess factors relevant to the LFLS model. To investigate the indirect effects of the five main predictors (paternal grandparents' circumcision attitudes, peer attitudes surrounding circumcision, father's HIV status, father's circumcision status, and mother's HIV status) on infant circumcision, a path analysis (Kline, 2011) will be conducted. To estimate the indirect effects, it will be specified that the paths between the five main predictors on infant circumcision will act through father's circumcision attitudes. Mother's circumcision attitudes will be regressed on mother's HIV status, and a regression path between father's and mother's attitudes toward circumcision will be specified. When estimating the indirect effects, results will be adjusted for the effect of number of siblings circumcised.

All potential indirect effects will be estimated by a bootstrapping approach (MacKinnon et al., 2007). R-square of indirect effects will be used as measures of effect size (Fairchild et al., 2009). A sandwich estimator will be used to account for the nested data structure (e.g., individuals are nested by clinics). This estimator uses the Huber/White correction and adjusts for potential underestimated standard errors and bias in chi-square computation (Liang & Zeger 1986).

Missing data will be handled using Full Information Maximum Likelihood estimation procedures (Enders & Bandalos 2001). For model fit evaluations, we will use well-established fit indices and cutoff values: A well-fitting model ideally will have a non-significant model χ^2 , a Comparative Fit Index / Tucker-Lewis Index greater than .95, a root mean square error of approximation less than .08, and a standardized root mean square residual less than .08 (Hooper et al., 2008). All analyses will be conducted in Mplus (V8; Muthén & Muthén, 2017).

H3. Effect of S&S + LFLS pilot. To compare the proportion of EIMCs in the experimental group to the proportion found in the observation group, a one-sample z-test will be conducted. The population proportion will be taken to be the midpoint of the findings from Waters et al. (2013) on neonatal circumcision and historical numbers of circumcisions from Zambian clinics and hospitals. Based upon this rationale, the percentage of EIMCs in the observation group is anticipated to be approximately 5.0%.

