Exploratory analyses. To investigate change in EIMC attitudes, Stages of Change scores will be examined over time using an autoregressive modeling approach specifying the individual's stage at 1-week postpartum as the main outcome and individual's stage at baseline as a main predictor in the regression model (Hamaker et al., 2015). Variables from the previous path model will be included as potential covariates in attempting to explain stage movement. The estimated regression coefficient will reflect changes in EIMC attitudes over time. The model will use an ordinal logistic model to examine change over time. Odd ratios will be estimated as a measure of effect size (Chen et al., 2010).

Power. Using a two-tailed Z test to test the difference in proportions between two conditions at an α level of .05, this study has over 80% power to detect a difference of 6.0% in EIMC rate between the two conditions. This difference in proportion translates to an effect size of an odds ratio (OR) = 2.4, which is considered a small (OR = 1.68) to medium (OD = 3.47) effect size, according to Chen et al. (2010). This 2.4 OR is based on an effect size found in previous research examining circumcisions ([name] et al., 2015). With these specified parameters, 80% power is achieved with 140 couples (out of ~151 couples with male infants).

Data Security. CAB and FGD participants will not provide any uniquely identifying information during participation in group discussion sessions. Pregnant couple participants in the intervention will be assigned a unique code upon entering the study. This number will identify all participant files, which will include no identifiable information. Access to the computer data files will be restricted by password codes. The list translating participant number to identifying information

IRB Study Number:

Version #, Date:

will be maintained in a secure locked file in the Spear & Shield study office in Lusaka at the University of Zambia School of Medicine. Participants will be made explicitly aware at the time of the informed consent of the nature of the separate record that will be kept for them. CAB and focus group discussions will be audio-taped for review and summary of key discussion points; copies will be stored in a locked cabinet at the PI's Lusaka offices, and deleted following summarization.

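### The Stages of Change model reads attitude change from the baseline-stage coefficient, which measures stability of ranking and not net change; the questionnaire's timing around LFLS Session 2 is also contradictory

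*Combined protocol and SAP*

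**What the plan says.** Section 14, Exploratory analyses, gives the aim as investigating change in EIMC attitudes. The model is an ordinal logistic autoregression that takes each person's "stage at 1-week postpartum as the main outcome" and baseline stage as the main predictor. On covariates it says: "Variables from the previous path model will be included as potential covariates in attempting to explain stage movement". On interpretation it says: "The estimated regression coefficient will reflect changes in EIMC attitudes over time". Odds ratios are to be the effect size. No time effect, paired comparison or table of stage transitions is specified.

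On dependence, section 14 under H2 says: "A sandwich estimator will be used to account for the nested data structure (e.g., individuals are nested by clinics"). The exploratory paragraph has no such statement and does not say whether mothers and fathers are analysed together.

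Section 11 lists as the secondary endpoint "Father's and mother's circumcision attitudes".

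On timing, section 12 (Couples Assessments) says: "After each LFLS session, a brief paper-based questionnaire will be individually administered to assess Stage of Change". The outline of LFLS Session 2 in the same section says: "Stages of Change questionnaires are administered prior to the session". The Session 1 outline and the closing paragraph of section 12 also put the questionnaire before the session. Couples Assessments schedules Session 2 for the neonatal visit in the first week after birth.

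**The concern.** The sentence on interpretation is singular, and baseline stage is the only predictor named as main, so the natural reading is that its coefficient will be reported as attitude change. That coefficient answers a different question: do people who started higher than others also finish higher than others? A test of whether its odds ratio equals 1 is a test of no association between the two measurements, not of no movement.

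If the coefficient is taken to mean the covariate effects instead, those describe who finishes higher among people with the same starting stage. They still do not estimate how far the group moved.

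Followed as written, the plan could report a significant odds ratio as change when the average stage rose, stayed level or fell. It could also report a null odds ratio as no change when many people advanced. No other stated analysis estimates attitude change. H2 uses attitudes as mediators, and the frequencies and means at the start of section 14 are there to check normality.

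The timing conflict adds a second ambiguity. If the questionnaire precedes Session 2, the one-week outcome reflects the four S&S sessions and LFLS Session 1, that is five of six sessions. If it follows, the outcome reflects all six. Clinics following different paragraphs would produce data that cannot be put right afterwards.

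**Working it through.** **No figure to reproduce.** The plan gives no sample size, power or effect size for this analysis. From the documents: five ordered stages (section 12, proposed assessments), 300 couples or 600 individuals at experimental clinics only (section 7), and the model in section 14. All correlations, cut points and shifts below are assumptions.

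**Algebra.** With baseline stage b and follow-up stage Y, the planned model is

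logit P(Y ≥ k | b) = α_k + β·b.

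If everyone shifts by δ on the logit scale, this becomes (α_k + δ) + β·b. The shift enters every threshold and β is unchanged. Hence exp(β) is the odds ratio of a higher follow-up stage per one-stage difference at baseline, whatever δ is. This follows from the model and needs no simulation.

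**Simulation 1: latent bivariate normal.** Cut points -0.8, -0.2, 0.4 and 1.0; n = 600; correlation 0.5; 60 runs per scenario. The uniform latent shift is -0.8, 0 or +0.8; the differential shift is +1.2 only below, or only above, the baseline median. The time odds ratio comes from a pooled proportional-odds fit of stage on time.

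| Scenario | Mean stage change | Baseline-stage OR | Time OR |
|---|---|---|---|
| Everyone falls | -0.95 | 1.91 | 0.26 |
| No net change | 0.00 | 1.96 | 1.00 |
| Everyone rises | +1.00 | 1.93 | 3.86 |
| Only low starters rise | +0.79 | 0.97 | 2.86 |
| Only high starters rise | +0.61 | 3.79 | 2.17 |

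In the three uniform scenarios the baseline-stage OR was significant in 100% of runs. Where only low starters rose it was significant in 5% of runs (repeat runs ranged up to 15%).

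Sensitivity of the baseline-stage OR, for fall / level / rise:
- correlation 0.3: 1.46 / 1.43 / 1.45
- correlation 0.7: 2.99 / 3.01 / 3.02
- correlation 0.5 with n = 300 (one parent per couple): 1.95 / 1.96 / 1.94

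The OR follows the assumed correlation, not the change.

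**Simulation 2: different assumptions.** Baseline stages 35/30/20/10/5%. Follow-up latent value = β·(b - 2.2) + shift + logistic error, cut at -1.0, 0.5, 2.0 and 3.5; n = 60,000. Cells show the baseline-stage OR, with mean stage change in brackets.

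| β | shift -1.5 | shift 0 | shift +1.5 |
|---|---|---|---|
| 0 | 0.99 (-0.67) | 1.00 (+0.05) | 1.01 (+0.96) |
| 0.5 | 1.65 (-0.65) | 1.66 (+0.07) | 1.65 (+0.94) |
| 1.0 | 2.73 (-0.57) | 2.74 (+0.09) | 2.72 (+0.93) |
| 1.5 | 4.47 (-0.47) | 4.50 (+0.13) | 4.56 (+0.89) |

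Along a row the group goes from regressing to advancing and the OR barely moves; at β = 1.0 the share advancing is 10%, 32% and 64%. Down the middle column net movement stays between +0.05 and +0.13 while the OR runs from 1.00 to 4.50. At β = 0 with shift +1.5, 63% advance and the OR is 1.01.

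**Timing.** Couples Assessments says after each session; both session outlines and the closing paragraph of section 12 say before. Session 2 falls in the same first post-partum week as the outcome, so the texts cannot both define the one-week measure.

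**The case against.** The strongest reply is that the planned model is not blind to change. The shift sits in its thresholds, and averaging its fitted probabilities recovers it: in the first simulation set-up this gave -0.94, +0.01 and +0.99 stage for the uniform scenarios, and +0.78 and +0.61 for the differential ones. That is correct, and it means a repeated-measures model is one good remedy and not the only one. But the plan does not propose to report thresholds or fitted movement. It names the regression coefficient and odds ratios.

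The analysis is labelled exploratory, tests neither H2 nor H3, and has no bearing on the power statement. This stands and limits the severity.

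Section 12 measures attitude items separately from Stages of Change, and section 11 lists attitudes, not change in them, so the link to the secondary endpoint is looser than it first looks. This stands in part, but the exploratory paragraph itself uses stage as its measure of attitude change.

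The sandwich estimator's position under H2 does not prove it is confined to H2. This also stands; the clear omissions are partner correlation and the pooling of parents.

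Finally, the simulations treat individuals as independent, and the analysed sample could be smaller: section 14 expects about 151 couples with male infants and does not say whether parents of girls contribute. Neither point affects the invariance of the coefficient.

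**Conclusion.** The concern holds. The stated interpretation is wrong, not merely incomplete. With a uniform shift, the baseline-stage odds ratio stayed between 1.91 and 1.96 while mean stage change ran from -0.95 to +1.00 (n = 600, assumed latent correlation 0.5). It was 0.97 when only low starters advanced and the mean rose by 0.79. The sizes rest on assumed inputs; the invariance to a uniform logit shift is a property of the proportional-odds model. The before/after contradiction on the questionnaire is plain on the page. Missing partner dependence and the unstated pooling of parents are secondary gaps. The matter should be corrected before analysis, and the timing before data collection.

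**What to change.** - Delete the sentence that equates the coefficient with change. Keep the baseline-adjusted model only for predictors of relative stage movement.
- Estimate change from the stage data already planned (baseline, Session 1, one week) with an ordinal repeated-measures model, GEE or mixed, in which time is the effect of interest. Report the time odds ratio with its confidence interval.
- State the dependence structure: repeated measures within person and partners within couple, or separate models for mothers and fathers. With only four experimental clinics, enter clinic as a covariate. State whether parents of girls are included.
- Reconcile the paragraphs of section 12 to one administration time, and state whether the one-week measure covers LFLS Session 2.
- State that the time effect is an uncontrolled before-after estimate and not an intervention effect, since section 12 (Design) says: "Participants will only be recruited from experimental sites".

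The cost is SAP wording and one further exploratory model, plus at most one extra administration of a brief paper questionnaire. The lack of a control group for this outcome remains.

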1) Demographics, to include gender, age, marital status, male children MC status, education, income, father's MC status, HIV status (All public health facility users are required to undergo HIV testing per GRZ policy) (adapted, Kabwe, 2016 and [name] et al., 2015).

2) Stages of Change EIMC items (Precontemplation, Contemplation, Preparation, Action, Maintenance) will be adapted from Redding et al. (2015).

3) EIMC knowledge, norms, attitudes/beliefs items (adapted from [name] et al., 2010; Chilimampunga et al., 2017; Kabwe, 2015; Mugyawana et al., 2011; Waters et al., 2013; Young et al., 2016).

4) VMMC knowledge, norms, attitudes/beliefs items will be evaluated using an adaptation of Kebaabetswe et al. (2003), [name] et al. (2015)

5) EIMC/LFLS Intervention acceptability and feasibility at the clinic level will be assessed using an adaptation of Chilimampunga et al. (2017) and Mavhu et al. (2015). Topics include review of the

IRB Study Number:

Version #, Date:

S&S+LFLS model, and the incorporation of EIMC services in the clinic, advantages and/or disadvantages of the program, and changes or recommendations for the program. Staff and CAB members will participate in clinic meetings to evaluate feasibility and acceptability of the S&S+LFLS program.

- 6) EIMC decision making will be assessed using items adapted from the conceptual model developed by Mavhu et al. (2017).
- 7) EIMC/VMMC Individual level Uptake. EIMC outcome, male infant; VMMC outcome, fathers and sons in the household, sex of infant & birth status (M/F; Live/Lost). VMMC/EIMC uptake and the role of parents, family members, peers and HIV serostatus in the decision-making process will be assessed by telephone or private office visit at 6 months post-partum.
- 8) EIMC/VMMC Clinic level Uptake. CHCs will provide 12 months of historical VMMC/EIMC rate data prior to VMMC/EIMC and S&S+LFLS training. Clinics will also collect real-time comparative VMMC/EIMC monthly aggregate data for the duration of the study (Monthly EIMC/VMMC conducted following EIMC/VMMC training (M6) to M30). Historical period: Monthly CHC EIMC/VMMC conducted for 1 year prior to EIMC/VMMC training.

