Following baseline assessments, couples will complete a brief Stages of Change questionnaire prior to each prenatal and one-week post-partum LFLS sessions. Couples will be assessed at 6 months post-partum to evaluate EIMC and VMMC uptake by father, sons and infant to examine the interactive influence of EIMC and VMMC uptake, as well as the role of both parents, family members, peers and HIV serostatus in the decision-making process (Montaño et al., 2018; Mavhu et al. 2017; Cook et al., 2015; [name], Cook et al., 2014) (see Assessments).

13) Data and Specimen Banking* n/a

14) Data Management*

Analytic Plan and Power Analysis

Aim 1. Develop, pilot and conduct formative, process and outcome evaluations to assess the CHC level feasibility and acceptability of S&S+LFLS.

Aim 2. Assess the intrapersonal, interpersonal, structural, and sociocultural factors relevant to the LFLS intervention, and develop program components to respond to these factors.

Hypothesis 2. Father's circumcision status, paternal grandparents' circumcision attitudes, peer circumcision attitudes, father's HIV status, and mother's HIV status will be indirectly related to the decision to choose EIMC through the father's circumcision attitudes. A mother's circumcision attitudes will be influenced by her HIV status, and her protective attitudes toward the newborn which will also influence the father's circumcision attitudes.

Aim 3. Assess whether the combined S&S + LFLS pilot program will increase uptake of EIMC at clinic level.

Hypothesis 3. The S&S + LFLS experimental condition clinics will have significantly higher numbers of EIMC in comparison with observation condition clinics.

Hypothesis testing. The analyses for this feasibility pilot study will begin with examination of frequencies, means, skewness, and kurtosis across study variables (EIMC, VMMC, HIV status, attitudes) to assess normality. We will conduct 1) analysis of qualitative data, 2) a path model to explore undergirding sociocontextual factors of a father's decision to elect EIMC or VMMC for his male children, 3) a test of comparison between conditions.

IRB Study Number:

Version #, Date:

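### The 80% power claimed for the two-condition EIMC comparison fits a one-sample test against a fixed 5% with independent infants, not a comparison of 4 with 4 randomised clinics

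*Combined protocol and SAP*

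**What the plan says.** The Power paragraph in section 14 (Data Management) describes a two-tailed Z test of the difference between two conditions at the 5% level. It states that "this study has over 80% power to detect a difference of 6.0% in EIMC rate between the two conditions", equates this with an odds ratio of 2.4, and adds that "80% power is achieved with 140 couples (out of ~151 couples with male infants").

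The H3 paragraph of the same section describes a different test. To compare the EIMC proportion "in the experimental group to the proportion found in the observation group, a one-sample z-test will be conducted". The reference value is external: "The population proportion will be taken to be the midpoint of the findings from" one earlier neonatal circumcision study and historical counts from Zambian facilities, giving roughly 5.0%.

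The design is a matched, clinic-randomised comparison of 4 with 4 (section 12, Design; section 24, Randomization). "Participants will only be recruited from experimental sites", and observation clinics supply aggregate counts only. Hypothesis 3, as worded in section 14, is that the "experimental condition clinics will have significantly higher numbers of EIMC in comparison with observation condition clinics". Section 12 also provides for clinic-level uptake: "Clinics will also collect real-time comparative VMMC/EIMC monthly aggregate data for the duration of the study".

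Nesting by clinic is recognised once, for the H2 path model: "A sandwich estimator will be used to account for the nested data structure". Neither the H3 test nor the power statement contains an ICC, a design effect or a clinic-level analysis.

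**The concern.** The power statement names a comparison that its 140 couples cannot supply, because all of them are in one condition. The test that the figure fits treats the comparator as a known constant and the infants as independent. Read literally, what happens in the randomised observation clinics never enters the H3 test.

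EIMC uptake is a primary endpoint (section 11), and H3 is the only between-condition hypothesis. All eight clinics receive EIMC training and equipment, so uptake could rise in both arms. The observation arm is there to separate that rise from the effect of S&S+LFLS. A test against a fixed 5% cannot do so. If clinics also differ in their underlying uptake, the unadjusted test has too small a standard error.

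The plan also does not say which observation-arm data H3 would use, or whether clinic-wide counts replace enrolled boys in the experimental arm. Power depends heavily on that choice.

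**Working it through.** **Inputs from the documents.** Two-sided alpha 0.05, a 6-point difference and 140 couples with male infants (Power paragraph); 5% comparator (H3 paragraph), hence 11% under the alternative; 4 + 4 clinics (section 12). The odds ratio for 5% vs 11% is (0.11/0.89)/(0.05/0.95) = 2.35, consistent with the stated 2.4.

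**Assumptions.** ICC 0.01, 0.02 and 0.05 (none is given). Equal numbers per experimental clinic, 140/4 = 35. Male births per clinic 150 × 0.5 × 18 months = 1,350, from the site criterion of more than 150 births a month (section 9).

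**1. Reproducing the plan's figure.** One-sample test against a fixed 5%:

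n = [1.96√(0.05×0.95) + 0.8416√(0.11×0.89)]² / 0.06² = 132.4

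Power at 140 = Φ{(0.06√140 − 1.96√0.0475)/√0.0979} = Φ(0.904) = 81.7%

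The exact binomial test (reject at 13 or more of 140) has 77.9%. With an odds ratio of exactly 2.4 (11.2%) and a continuity correction, the required n is 139.9, which is the stated 140.

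**2. Two-sample tests, independent infants.** With 140 per arm, power is 46%, and 320 per arm are needed for 80%. With 140 against 4 × 1,350 = 5,400 observation births, pooled power is 80.5%. Sampling error in the observation arm is therefore a minor omission if its denominator is large.

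**3. One-sample test with clustering in the 4 experimental clinics.** Design effect 1 + 34×ICC = 1.34 / 1.68 / 2.70; effective n = 104 / 83 / 52. If clustering is ignored, type I error by normal approximation is 2[1 − Φ(1.96/√design effect)]. A beta-binomial simulation is more reliable here, since only 7 events are expected under the null.

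**4. Clinic-level comparison, 4 vs 4.** Variance per clinic V = p(1−p)[(1−ICC)/m + ICC]; SE = √[(V_E + V_O)/4]; noncentral t with 6 df and noncentrality 0.06/SE.

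- Case (a): 35 enrolled boys per experimental clinic vs 1,350 births per observation clinic.
- Case (b): clinic-wide counts, 1,350 per clinic in both arms, with the full 6-point effect clinic-wide.

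Example, case (a), ICC 0.01: V_E = 0.0979 × 0.03829 = 0.003748; V_O = 0.0475 × 0.01073 = 0.000510; SE = √(0.004258/4) = 0.0326; 0.06/0.0326 = 1.84; power 34%; 95% CI half-width 2.447 × 0.0326 = 8.0 points.

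| ICC | One-sample power, clustering allowed for | Type I error if ignored: simulated (normal approx.) | (a) power; half-width | (b) power; half-width |
|---|---|---|---|---|
| 0.01 | 72% | 6% (9%) | 34%; 8.0 pts | 72%; 4.8 pts |
| 0.02 | 65% | 9% (13%) | 27%; 9.2 pts | 45%; 6.7 pts |
| 0.05 | 51% | 16% (23%) | 17%; 12.2 pts | 22%; 10.5 pts |

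The simulated type I error at ICC 0 is 3%. At ICC 0, case (a) has 47% power and case (b) nearly 100%. Case (b) has 93% at ICC 0.005 and falls to 80% at about 0.008. With 3 df (matched pairs, no precision gain assumed), (a) is 25% / 20% / 14% and (b) is 54% / 33% / 17%. Replacing 1,350 by 900 or 1,800 in case (b) changes 6-df power by less than 1.5 points at these ICCs.

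**5. Dilution in case (b).** A 6-point effect confined to enrolled couples moves the clinic-wide rate by only 0.06 × 35/1,350 = 0.16 points.

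**6. Leaving out the observation arm.** The fixed-5% test rejects upward above 0.05 + 1.96√(0.0475/140) = 8.61%. If both arms are truly at 7%, the chance of that is 1 − Φ[(0.0861 − 0.07)/√(0.07×0.93/140)] = 1 − Φ(0.75), about 23% (independent infants).

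**The case against.** **The one-sample origin is inferred.** The plan does not show how 140 was obtained, and 140 boys against several thousand observation births also gives just over 80%. That is so, and the figure can only be said to match the one-sample test. The alternative reading still treats infants as independent and contradicts the H3 paragraph.

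**The ICCs are assumed, and clinic-wide counts could be adequate at a low ICC.** This stands as a limit on the size. It does not rescue the claim: case (a) has only 47% power at ICC 0, case (b) needs the whole clinic population to shift, and the plan does not say which applies.

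**The observation rate could be far below 5%.** The background sections cite about 0.3% nationally. At 0.3% vs 6.3%, the step 4 formula gives 97% / 80% / 44% for (b) and 56% / 47% / 31% for (a). So the results do depend on the plan's own 5%. In that same scenario, however, the planned test compares 6.3% with 5% and rejects upward with probability only 1 − Φ[(0.0861 − 0.063)/√(0.063×0.937/140)] = 1 − Φ(1.125), about 13%.

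**Matching and 12 months of historical data could raise precision.** They could. The figures above are unadjusted, and the plan specifies no adjusted analysis for H3.

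**This is a feasibility pilot.** Low power is acceptable in a pilot, and Hypothesis 3 in the Objectives omits the word significantly. Section 14 nevertheless states a significance hypothesis and a power claim.

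**Conclusion.** The concern holds. The arithmetic behind 140 is sound for a one-sample test of 11% against a fixed 5% with independent infants (81.7%), but the plan presents it as power between two randomised conditions. That mismatch, and the absence of any clinic-level allowance in H3, can be seen in the text without assumptions.

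For the comparison Hypothesis 3 describes, unadjusted power at a 5% observation rate is 17% to 34% with enrolled boys in the experimental arm, or 22% to 72% with clinic-wide counts, over assumed ICCs of 0.05 to 0.01. The enrolled-boys shortfall remains at ICC 0. The clinic-wide figures reach 80% only at an ICC of about 0.008 or less and need a full clinic-wide effect. Inflation of the type I error is modest at ICC 0.01 (about 6%) and clear at 0.05 (about 16%). This must be fixed, because the planned test does not test the stated hypothesis.

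**What to change.** Amend the H3 and Power paragraphs of section 14 together.

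- **H3:** base the between-condition comparison on the 4 experimental and 4 observation clinics. State the numerator and denominator in each arm: enrolled male infants or clinic-wide counts. State whether the matching and the historical 12 months enter the analysis. If the comparison with 5% is kept, label it a benchmark for the experimental arm.
- **Power:** state that 80% applies only to independent infants compared with a fixed 5%, and withdraw the claim of over 80% power between conditions. Report 4-versus-4 power, or the expected confidence-interval width, over a stated ICC range.

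The cost is wording and one clinic-level analysis, with no additional enrolment. The stated power will look less favourable. One data item needs checking: section 12 lists monthly procedures but not monthly male births, so a proportion for the observation clinics may need birth counts from those sites.
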